### **4.6 TREATMENT, PATIENT, STUDY, AND SITE DISCONTINUATION**

#### **4.6.1 Study Treatment Discontinuation**

Patients must permanently discontinue study treatment if they experience any of the following:

- Any medical condition that the investigator or Sponsor determines may jeopardize the patient's safety if he or she continues to receive study treatment
- Investigator or Sponsor determination that treatment discontinuation is in the best interest of the patient
- Pregnancy
- Use of an anticancer therapy not required per protocol
- Symptomatic deterioration attributed to disease progression
- Confirmed disease progression per investigator assessment according to IMWG Uniform Response Criteria ([Appendix 5](#))
- Patient decision

The primary reason for study treatment discontinuation should be documented on the appropriate eCRF. Patients who discontinue study treatment prematurely will not be replaced unless enrolled in the dose-escalation cohorts and discontinue prior to completion of the 14-day DLT assessment window.

Patients will return to the clinic for a treatment discontinuation visit 30 ( $\pm$  10) days after the final dose of study drug (see [Appendix 1](#) for additional details). Additionally, patients who discontinue study treatment for reasons other than documented disease progression or relapse should continue to be followed as described in [Appendix 2](#) until disease progression, start of new anti-cancer therapy, or withdrawal from study participation, whichever occurs first.

#### **4.6.1.1 Survival and Subsequent Anti-Cancer Therapy Follow-Up**

Following study treatment discontinuation (initial or after re-treatment), patients may be followed for survival and subsequent anti-cancer therapy. Survival and subsequent anti-cancer therapy follow-up information may be collected via telephone calls, patient medical records, and/or clinic visits approximately every 3 months until death, loss to follow-up, or study termination by the Sponsor unless the patient requests to be withdrawn from follow-up. Information on subsequent anti-cancer therapies will include systemic therapies (e.g., chemotherapy, targeted therapy, hormonal therapy), surgery (e.g., resection of metastatic disease), and radiation procedures (radiotherapy to a tumor lesion). If the patient withdraws from the study, the site's staff may use a public information source (e.g., county records) to obtain information about survival status only.

#### **4.6.2 Patient Discontinuation from the Study**

Patients have the right to voluntarily withdraw from the study at any time for any reason. In addition, the investigator has the right to withdraw a patient from the study at any time.

Reasons for patient discontinuation from the study may include, but are not limited to, the following:

- Patient withdrawal of consent
- Study termination or site closure
- Loss to follow-up
- Patient non-compliance, defined as failure to comply with protocol requirements as determined by the investigator or Sponsor

Every effort should be made to obtain a reason for patient discontinuation from the study. The primary reason for discontinuation from the study should be documented on the appropriate eCRF. If a patient requests to be withdrawn from the study, this request must be documented in the source documents and signed by the investigator. Patients who withdraw from the study will not be replaced unless enrolled in the dose-escalation cohorts and discontinue prior to completion of the 14-day DLT assessment window.

If a patient withdraws from the study, the study staff may use a public information source (e.g., county records) to obtain information about survival status.

#### **4.6.3 Study Discontinuation**

The Sponsor has the right to terminate this study at any time. Reasons for terminating the study may include, but are not limited to, the following:

- The incidence or severity of adverse events in this or other studies indicates a potential health hazard to patients.
- Patient enrollment is unsatisfactory.

The Sponsor will notify the investigator if the Sponsor decides to discontinue the study.

#### **4.6.4 Site Discontinuation**

The Sponsor has the right to close a site at any time. Reasons for closing a site may include, but are not limited to, the following:

- Excessively slow recruitment
- Poor protocol adherence
- Inaccurate or incomplete data recording
- Non-compliance with the International Council for Harmonisation (ICH) guideline for Good Clinical Practice
- No study activity (i.e., all patients have completed the study and all obligations have been fulfilled)

### **5. ASSESSMENT OF SAFETY**

#### **5.1 SAFETY PLAN**

This is the first study in which RO7297089 will be administered to humans. As such, the actual risks are unknown. The following information describing monitoring and management of potential safety risks is based on anticipated pharmacology and mechanism of action, results from nonclinical studies, and published data on similar molecules. Please refer to the RO7297089 Investigator's Brochure for further safety information.

Measures will be taken to ensure the safety of patients participating in this trial, including the use of stringent inclusion and exclusion criteria (Sections 4.1.1 and 4.1.2) and close monitoring, as described below. As described in Section 3.1.1, enrollment of the first patient in each *arm in each* dose-escalation cohort will be staggered such that the respective Cycle 1, Day 1 treatments are administered  $\geq 72$  hours apart.

After each patient receives the first dose of RO7297089, the investigator should confirm with the Sponsor that the patient has been dosed and should provide a brief summary of the status of the patient in terms of safety and tolerability to RO7297089 (this will be communicated by email and/or telephone; as soon as reasonably possible). In addition, regularly scheduled teleconferences will occur with the investigators and study team (including the Medical Monitor and Safety Scientist) to review the following for each patient: all relevant demographic, adverse event, laboratory, dose administration, available (radiographic) response, and available PK and PD data (e.g., imaging, plasma cytokines and markers of NK-cell activation).

All patients will be monitored closely for toxicity. Patients will be assessed clinically for toxicity prior to each dose using the NCI CTCAE v5.0 grading scale, except for CRS, in which the Modified Cytokine-Release Syndrome Grading System will be used (see [Appendix 9](#)). All adverse events and serious adverse events will be recorded during the trial and for up to 90 days after the final dose of study treatment or until the initiation of another systemic anti-cancer therapy, whichever occurs first. To mitigate potential

unknown risks, at least in part, dosing beyond Cycle 1 will be limited to patients who do not demonstrate unacceptable toxicity or compelling evidence of disease progression (see Section 3.1.1.2).

Specific anticipated or potential toxicities associated with administration of RO7297089, as well as the measures taken to avoid or minimize such toxicities in this trial, are described in the following sections.

## **5.1.1 Potential Risks Associated with RO7297089**

### **5.1.1.1 Infusion-Related Reactions/Cytokine-Release Syndrome**

The mechanism of action of RO7297089 is engagement and activation of NK cells against cells expressing BCMA. Therefore, a spectrum of events involving IRRs, CRS, and/or hypersensitivity with or without emergent ADAs, may occur. These reactions may be mild in severity but can also be severe or even fatal. Common signs and symptoms of these reactions could include fever; chills or rigors; alteration in heart rate and blood pressure; dyspnea or chest discomfort; back or abdominal pain; nausea, vomiting, and/or diarrhea; and various types of skin rash. Severe reactions can also include hypotension, hypoxia, other organ dysfunction, and/or neurologic toxicity.

In nonclinical studies, cytokine release with RO7297089 was assessed both in vitro as well as in the toxicity studies in cynomolgus monkeys. Clinical findings consistent with CRS and/or increases in inflammatory cytokines associated with CRS (e.g., IL-6, TNF- $\alpha$ , IFN- $\gamma$ ) due to RO7297089 were not observed in cynomolgus monkeys. IRRs were not observed in cynomolgus monkeys. In vitro studies at clinically relevant concentrations of RO7297089 in the presence of human PBMCs and MMCs expressing BCMA demonstrated minimal increases in inflammatory cytokines consistent with pharmacology. The changes were similar in magnitude to that seen with daratumumab, and were far lower than levels seen with T-cell engaging bispecific antibodies in similar assays.

Other bispecific antibody therapeutics involving NK-cell activation have been associated with IRRs in patients, though CRS was not demonstrated clinically. AFM13 is a tetravalent bispecific antibody with a mechanism of action similar to RO7297089, except that it engages NK cells to target CD30 expressed on B cells in patients with Hodgkin lymphoma and some types of non-Hodgkin lymphoma. In patients with R/R Hodgkin lymphoma treated with single-agent AFM13 in a dose-escalation Phase I study, Grade 1–2 IRRs were seen in 4 patients (14%) and CRS was not reported (Rothe et al. 2015).

Based on these nonclinical data, experience with molecules with a similar mechanism of action, and clinical experience with RO7297089 to date, RO7297089 has the potential to cause an IRR and/or CRS, but the likelihood of CRS appears very low (see Section 1.2). *In this current first-in-human, dose-escalation Study GO41582, the observation of IRR events led to the release of an Urgent Safety Measure (USM) on*

4 September 2020 and a subsequent protocol amendment to mandate premedication with corticosteroids. At the time of the USM, 1 of 3 patients in Cohort 1 (60 mg) and 2 of 2 patients in Cohort 2 (180 mg) experienced a Grade 2 IRR in Cycle 1. The IRR events, consisting of shivering/rigors and temperature elevation, occurred either during the infusion or during the post-infusion observation window. To minimize the risk of IRRs, patients will be premedicated prior to the first administration of RO7297089 for Arms A and B, and prior to the first two doses of RO7297089 for Arm C, unless contraindicated (see Section 4.3.2.1). Administering premedication on the day prior to infusion may also be considered and/or implemented to mitigate IRR. Patients will be dosed slowly over a minimum of 2 hours to mitigate IRR and monitored closely for 4 hours following their first infusion of RO7297089 (see Table 1), with frequent vital sign measurements (see Table 2) to identify potential IRR/CRS. Patients who tolerate RO7297089 infusions well do not require as long an infusion time or observation period with subsequent infusions and will be observed post-infusion as described in Table 1.

Guidelines for management of patients who develop an IRR are summarized in Table 3, with grading according to NCI CTCAE v5.0. Management of Grade  $\geq 3$  IRR should be immediately discussed between the treating investigator and the Medical Monitor. Refer to Section 5.3.5.1 for adverse event reporting procedures related to IRRs. Guidelines for management of and grading of CRS according to the Modified Cytokine-Release Syndrome Grading System (Appendix 9) are summarized in Appendix 10.

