## PROTOCOL HISTORY

Protocol		Associated Country-Specific Protocols		
Version	Date Final	Country	Version	Date Final
4	See electronic date stamp on title page	—	—	—
3	18 September 2020	—	—	—
2	23 April 2020	Belgium	2	30 July 2020
		Norway	2	10 May 2020
1	25 November 2019	—	—	—

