### **2.1 SAFETY OBJECTIVE (PRIMARY STUDY OBJECTIVE)**

The safety objective for this study is to evaluate the safety of RO7297089, including estimation of the MTD and characterization of dose-limiting toxicities (DLTs), on the basis of the following endpoints:

- Incidence and severity of adverse events, including DLTs, with severity determined according to National Cancer Institute Common Terminology Criteria for Adverse Events, Version 5.0 (NCI CTCAE v5.0) and the Modified Cytokine-Release Syndrome Grading System ([Appendix 9](#))
- Change from baseline in targeted vital signs
- Change from baseline in targeted ECG parameters
- Change from baseline in targeted clinical laboratory test results
- Relationship between RO7297089 dose and safety, PK, activity, and immunogenicity endpoints

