*Dedicated dose-escalation arms have been added to evaluate split-dose and step-dose administration schedules with regard to mitigating the risk of IRRs. While the impact of these alternate dose administration schedules on the frequency and severity of IRR is unknown for RO7297089, similar interventions have been successful with other monoclonal antibody therapies.*

Details of nonclinical studies described above, starting dose rationale, and human equivalent dose calculation can be found in RO7297089 Investigator's Brochure.

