#### **4.3.2.1 RO7297089**

Dosing independent of body weight will be used for RO7297089. The dose of RO7297089 for each patient will depend on the dose level assignment as detailed in the protocol.

In this study, RO7297089 will be administered to patients by IV infusion using standard syringes and syringe pumps or IV bags where applicable. The drug product will be delivered by syringe pump via an IV infusion set or IV bag with a final RO7297089 volume determined by the dose. The specific RO7297089 dose will determine the appropriate dosing concentrations, volumes, and infusion times, and will also dictate the specific, appropriate, administration apparatus (i.e., peripheral catheter vs. syringe pump vs. IV bags) to be used. Premedication with oral acetaminophen or paracetamol (e.g., 500–1000 mg), an antihistamine (25–50 mg diphenhydramine or equivalent), and a corticosteroid (minimum equivalent of 80 mg IV methylprednisolone) will be administered as prophylaxis for IRR prior to first administration of RO7297089 *for Arms A and B, and prior to the first two doses of RO7297089 for Arm C, unless contraindicated. Administering premedication on the day prior to infusion may also be considered and/or implemented to mitigate IRR.* Premedication may be given prior to subsequent infusions at the discretion of the investigator. All RO7297089 doses should be administered to well-hydrated patients.

Recommended management of IRR is detailed in Section 5.1.2.2.

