## **6. STATISTICAL CONSIDERATIONS AND ANALYSIS PLAN**

No formal hypothesis testing is planned. Descriptive statistics will be used to summarize the safety, tolerability, pharmacokinetics, and clinical activity of RO7297089. Data will be described and summarized as warranted by number of patients in question. Listings will be used in place of tables for small numbers of patients. All analyses will be based on the safety-evaluable population, defined as all patients who receive any amount of study drug.

Continuous variables will be summarized using means, standard deviations, median and ranges; categorical variables will be presented using counts and percentages. All summaries will be presented by dose cohort to which a patient was originally assigned.

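### Corticosteroid premedication became mandatory partway through escalation, so mandated cover follows dose, and IRR summaries grouped only by dose cohort cannot separate the two

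*Combined protocol and SAP*

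**What the plan says.** Section 5.1.1.1 gives the Cycle 1 counts known when the USM was issued: "1 of 3 patients in Cohort 1 (60 mg) and 2 of 2 patients in Cohort 2 (180 mg) experienced a Grade 2 IRR". It adds that the USM was followed by "a subsequent protocol amendment to mandate premedication with corticosteroids". The first protocol version dated after the USM is Version 3, "18 September 2020" (Protocol History).

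Under the current rule in Section 4.3.2.1, "a corticosteroid (minimum equivalent of 80 mg IV methylprednisolone) will be administered as prophylaxis for IRR prior to first administration of RO7297089". The mandate covers the first administration in Arms A and B and the first two doses in Arm C, unless contraindicated. Later premedication is left to the investigator.

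On analysis, Section 6 says: "All summaries will be presented by dose cohort to which a patient was originally assigned". Section 6.4.1 describes the adverse event summaries without a split by premedication, protocol version or arm. No hypothesis test is planned.

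Two stated aims depend on these summaries. Section 2.1 lists this endpoint under the primary objective: "Relationship between RO7297089 dose and safety, PK, activity, and immunogenicity endpoints". Section 3.3.2 says: "Dedicated dose-escalation arms have been added to evaluate split-dose and step-dose administration schedules with regard to mitigating the risk of IRRs". Those arms came in with Version 4, after the mandate.

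**The concern.** Escalation runs in calendar order, so a rule introduced partway through is tied to dose. The three reported 60 mg patients preceded the mandate. Two 180 mg patients had been reported by then, and Section 3.1.1 requires at least three per cohort, so Cohort 2 is mixed. Higher doses follow. A table of IRRs by dose cohort therefore compares doses under different mandated steroid cover. If steroids reduce IRRs, a real rise with dose can be hidden, or a fall can appear where dose has no effect.

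This bears on more than presentation. Section 3.1.1.1 keeps Grade 3 IRRs out of the DLT definition on the premise that IRRs are generally not dose-related, citing experience with monoclonal antibodies. The trial's own description of IRR by dose is the natural check on that premise, and the planned grouping could support it falsely. Because no testing is planned, the descriptive tables are the main evidence on this question.

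**Working it through.** The plan gives no target or planning figure for IRRs, so there is nothing to reproduce. The check asks what the planned grouping would display under stated assumptions.

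**From the documents:** IRR counts at the USM (Section 5.1.1.1); minimum cohort size 3 (Section 3.1.1); grouping by dose cohort (Section 6).

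**Assumed:** IRR risk without steroid p0 = 0.4 to 0.8; steroid risk ratio RR = 0.3 to 0.7; the five reported patients uncovered; one further patient at 180 mg, covered; all patients at higher doses covered.

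**1. What the five patients show.** Exact 95% intervals:
- 60 mg, 1/3: 33% (0.8% to 90.6%)
- 180 mg, 2/2: 100% (15.8% to 100%)
- Both, 3/5: 60% (14.7% to 94.7%)

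Fisher's exact p for 60 v 180 mg is 0.40. These counts alone settle nothing about dose.

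**2. No true dose effect.** Expected displayed rates:
- 60 mg: p0
- 180 mg: (2·p0 + 1·p0·RR)/3
- Higher doses: p0·RR

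With p0 = 0.6 and RR = 0.5 these are 60%, (1.2 + 0.3)/3 = 50%, and 30%. The false fall from 60 mg to higher doses is p0(1 − RR). Over the assumed ranges it runs from 0.4 × 0.3 = 12 points to 0.8 × 0.7 = 56 points.

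**3. True gradient.** Take uncovered risks of 33%, 60% and 80%. The display is 0.33, then (2 × 0.6 + 0.6·RR)/3, then 0.8·RR.

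| RR | 60 mg | 180 mg | Higher | If all were covered |
|---|---|---|---|---|
| 0.3 | 33% | 46% | 24% | 10 / 18 / 24% |
| 0.5 | 33% | 50% | 40% | 17 / 30 / 40% |
| 0.7 | 33% | 54% | 56% | 23 / 42 / 56% |

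At RR 0.3 the order of the lowest and highest doses reverses. At 0.5 the rise is largely masked. At 0.7 it survives but shrinks, from 33 points with everyone covered (23% to 56%) to 23 points displayed.

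**4. Arms.** If all flat-dose patients (5 uncovered plus k covered) were pooled as Arm A and set against fully covered Arms B and C, with no true arm effect, the false advantage is 5/(5 + k) × p0(1 − RR). With p0 = 0.6 and RR = 0.5 it is 25.0 points (k = 1), 16.7 (k = 4), 10.0 (k = 10) and 7.1 (k = 16). Over the assumed ranges and k from 1 to 16, it is 2.9 to 46.7 points. Within a dose cohort opened after the mandate no Arm A patient predates it, and this bias is 0. A difference in cover remains: on Cycle 1 Day 8, when all three arms give the full target dose, the mandate reaches Arm C only.

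**The case against.** The strongest reply is that the plan promises little here. Section 6 is descriptive, tests nothing, and uses listings in place of tables for small numbers, so two or three early patients may be shown individually. Section 5.1 has the sponsor and investigators reviewing each patient's adverse events and dosing. Grade 2 IRRs are not DLTs, and Arms B and C open on infusion time or on IRRs that prevent full dosing, not on IRR rates compared between arms. All of this stands and limits the consequences. It does not remove the confounding: nothing in Section 6 requires a listing or table to show steroid cover.

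Four stronger readings are tempting and not supported.

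- *That the plan contains a biased comparison of Arm A with Arms B and C.* Section 6 specifies no such comparison. Section 3.3.2 states an aim, and bias from pre-mandate patients arises only if Arm A is pooled across cohorts.
- *That early and late patients are pooled throughout.* Mixing within a dose level is limited to Cohort 2 and any backfill at 60 or 180 mg. Elsewhere the confounding is between cohorts.
- *That the five patients had no steroid.* The documents say only that it was not yet mandated. Five is also the count at the USM; others may have been dosed before the amendment took effect.
- *That the observed 2/2 at 180 mg measures the bias.* Adding one covered patient at an assumed 25% risk gives (2 + 0.25)/3 = 75% against 25%, an apparent 50-point steroid artefact. That formula has no steroid effect in it and would give 75% if steroids did nothing. In expectation, with p0 = 0.6 and RR = 0.5, the gap is (2/n) × 0.3: 20 points at n = 3 and 10 at n = 6. It also presumes Arm B at 180 mg, which the documents do not show. At the 14 mg/kg/hr limit an assumed 60 kg patient needs 180/(14 × 60) = 0.21 hours, about 13 minutes. The 2-hour minimum therefore governs, and the 4-hour trigger would be met only if infusion were deliberately lengthened.

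**Conclusion.** The concern holds as a reporting problem. If Section 6 is followed as written, the description of IRR by dose is confounded with mandated steroid cover. The direction is predictable if steroids reduce IRRs: rates at higher doses look lower relative to 60 mg than they would under equal cover. With no dose effect the false fall is 12 to 56 points over the assumed ranges, 30 points at the central values. These sizes rest on assumed risks, an assumed steroid effect and the assumption that the five reported patients were uncovered; post-mandate counts are not in the documents.

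For the arms the conclusion is conditional. There is no bias from pre-mandate patients within cohorts opened after the mandate, and a false advantage for split or step dosing if early flat-dose patients are pooled into Arm A. The unequal mandate on Day 8 affects even the within-cohort description.

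The dose-escalation model is little affected. Grade 2 and 3 IRRs do not count as DLTs unless a recurrence precludes dosing.

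**What to change.** Add to Section 6.4.1 that IRR incidence and severity will be summarised by dose level and arm, split by whether a corticosteroid was actually given before that infusion. If that cannot be established, split by dosing before or after the mandate took effect. The fallback is weaker: it does not capture discretionary use, contraindications, or Arm C's second mandated dose.

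Show pre-mandate patients as a separate stratum rather than dropping them, since exclusion would remove the whole initial 60 mg cohort from the dose description. Limit any description of Arms A, B and C against each other to steroid-covered infusions at the same dose.

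Confirm that the eCRF records premedication by infusion. Section 4.4 defines concomitant therapy as additional to protocol-mandated treatment, so mandated premedication may not be captured on that form.

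The cost is one sentence and one table with small cells. There will be little or no steroid-covered 60 mg data unless backfill occurs, so the steroid-covered dose comparison may in practice start at 180 mg. No dose, schedule or management rule changes.
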